### 2. Study Design

### 2.1 Study Overview

The objective of study is to assess the efficacy of electro-acupuncture (EA) for opioid-induced constipation(OIC) in adult patients with cancer pain.

### 2.2 Background

In advanced diseases, 70-80% of patients experience moderate to severe pain. As the cornerstone of treatment for moderate to severe cancer pain, opiate analgesics, such as morphine and oxycodone, are recommended by WHO Cancer Pain Relief Guidelines . The use of systemic opioids is recommended by some studies for cancer patients

7

experiencing moderate to severe pain, regardless of the underlying causes. Opioids stimulate receptors both in the central nervous system (CNS) and the peripheral nervous system, reducing pain and improving quality of life for patients. The drug can, however, be associated with serious adverse events (AEs) with a rate ranging from 1.8% to 13.6%, the most common of which is opioid-induced constipation (OIC). OIC represents a change in baseline bowel habits or defecation patterns that occurs following the administration or modification of opioid therapy 8-10. Approximately 41% of non-cancer patients and 94% of cancer patients who use opioids for pain have this condition . Symptoms of OIC are usually persistent and difficult to tolerate , which adversely affects patients' quality of life and results in reductions in dose or discontinuation of opioid analgesics . OIC is the result of multiple factors contributing to it : Opioids may activate u-receptors throughout the gastrointestinal tract and cause changes to gut motility, decreases in gut secretion, and an increase in sphincter tone, which can lead to constipation . Various pharmacological and nonpharmacological interventions are used to manage OIC, such as laxatives and increased fluid intake 8-9. 19. However, these interventions are limited in effectiveness, and they do not address the pathophysiological mechanisms of OIC . Several peripherally acting μ-opioid receptor antagonists (PAMORAs), such as naloxegol and methylnaltrexone, have recently been shown to be effective in treating OIC patients who do not respond to simple medications . However, longer-term efficacy and safety of PAMORAs are unclear, and they haven't been approved in China yet. Clinical trials are still underway to test these drugs. Additionally, PAMORAs are often associated with AEs such as abdominal pain and flatulence. As a result, it is still necessary to explore new treatment approaches for OIC.

In traditional Chinese medicine, acupuncture has been used to treat gastrointestinal disease, including constipation, for thousands of years. According to two systematic reviews, acupuncture can improve spontaneous bowel movements (SBMs) in functional constipation . Additionally, the results of our study indicated that electroacupuncture (EA) could increase complete spontaneous bowel movements (CSBMs) and SBMs, with a long-term effect that continues for 24 weeks after treatment ceased among patients with chronic, severe functional constipation . Through stimulation of the somatic and peripheral nervous systems, acupuncture can facilitate the gut motility and improve

gastrointestinal function . The effectiveness of acupuncture for OIC is currently lacking evidence. The purpose of this study is to compare the efficacy and safety of EA with sham acupuncture (SA) in the treatment of OIC in cancer patients.

### 2.3 Study Hypothesis

We hypothesize that EA is better than SA in treating OIC in adult patients with cancer pain.

### 2.4 Methodology

### 2.4.1 Trial Design

This is a multicenter, prospective, sham-controlled, parallel-group, subject- and assessor-blinded, randomized trial at 7 centers in China. Cancer patients must meet the Rome IV diagnostic criteria for OIC.

### 2.4.1.1 Randomization

Web-based central randomization will be performed by the Linkermed Pharm Technology Co. Ltd (Beijing, China). Participants will be randomly allocated, in a 1:1 ratio, to either the EA or the SA group using permuted block-randomization. Acupuncturists in each center will be responsible for getting random numbers. Via inputting the screening information of the participant in the central randomization system through the web, they will get the random number and group allocation.

### **2.4.1.2 Blinding**

In this study, participants, outcome evaluators, and data analysts will be blinded to the group assignments. The acupuncturists who perform the treatment will not be blinded due to the nature of the acupuncture treatment. Participant blinding will be achieved via a minimal needling at non-acupoints. Bilateral sham points will be attached with the same EA apparatus using a continuous wave of 10Hz and a current intensity of 0.1–0.2mA for 30 minutes after a brief activation period of 30 seconds.

For blinding assessment, all participants will be requested to answer the following question: "Is EA the acupuncture modality that you have received?" within five minutes after any treatment at week 8.

### **2.4.1.3 Sample Size**

On the basis of unpublished data, a 14% response rate was assumed for the sham acupuncture group in this study. We estimated that a sample size of 100 participants would provide 90% power to detect a between-group difference of 31.4% at the two-sided significance level of 0.05 and 20% loss to follow-up.

### 2.4.2 Subjects

Participants with cancer will be publicly recruited from inpatient and outpatient departments through posters and networks from 6 centers in China.

### 2.4.2.1 Inclusion Criteria

(1) Cancer patients must meet the Rome IV diagnostic criteria for OIC. Participants have at least 2 of the following new or worsening symptoms of constipation following initiation, alteration, or increase in opioid treatment: fewer than three SBMs per week, straining (>25% of defecations), sensation of incomplete evacuation (>25% of defecations), lumpy or hard stools (>25% of defecations), and/or sensation of anorectal obstruction/blockage (>25% of defecations). For patients with a history of chronic functional constipation, he/she must have worsening symptoms of constipation when the opioid therapy is initiated, changed, or the dose is increased; (2) Patients recruited in this trial must have a history of OIC symptoms for at least 1 week; (3) Patients must be  $\geq 18$ years of age and ≤85 years of age; (4) Patient's cancer condition must be stable with a life expectancy that is more than six months; (5)Patients must have an Eastern Cooperative Oncology Group (ECOG) performance status of 0-3; (6) Patients must have been receiving a stably maintained opioid regimen, consisting of a total daily dose of 30 mg to 1000 mg oral morphine equivalents for at least 2 weeks prior to screening for cancer pain. Furthermore, it must be anticipated that the opioid will be maintained for at least 10 weeks; (7) The SBM frequency of the patients must be 2 times a week when laxatives are not being taken: (8) Patients must be capable of oral intake of drugs, food and beverages; (9)Provision of written informed consent before inclusion.

### 2.4.2.2 Exclusive Criteria

Participants will be excluded from this trial if they have any of the following conditions:

(1) Patients diagnosed with clinically significant abnormal defecation due to functional

disorders or structural abnormalities of the gastrointestinal tract and other tissues related to gastrointestinal tract (not including OIC): inflammatory bowel disease, rectal prolapse, gastrointestinal obstruction, peritoneal metastasis, or peritoneal tumor at the time of enrollment; (2)Patients with a history of gastrointestinal tract operation, abdominal operation, or abdominal adhesion within one month prior to screening; history of intestinal obstruction within three months prior to screening; (3) Diagnosis of active diverticular disease; or severe hemorrhoid; or anal fissure; or artificial rectum or anus; (4) Patients with an intraperitoneal catheter or those that use a feeding tube to maintain vital signs; (5) Diagnosis of pelvic disorder, which are considered to have obvious effects on the intestinal transport of feces (such as uterine prolapse ≥degree 2, uterine fibroids [located in the posterior of the uterus with a diameter  $\geq 5$  cm] affecting bowel movement); (6)Patients that are being treated with a new cancer chemotherapy, which had never been administered in the past, within 14 days of the screening or are scheduled to receive such therapy during the study; (7) Patients that received radiotherapy within 28 days of the screening or are scheduled to receive such therapy during the study; (8)Patients that underwent a surgery or intervention that is considered to have an obvious effect on the gastrointestinal functions within 28 days of the screening or are scheduled to receive surgery or intervention which is considered to have obvious effects on the gastrointestinal functions during the study, or scheduled to receive surgery or intervention which will be anticipated to prevent the patients from completing the trial; (9) Patients with uncontrolled hyperthyroidism, severe hypertension, heart disease, systematic infection or blood coagulation disorders (hypercoagulation status or hemorrhagic tendency); (10)Patients that consumed >4 additional opioid doses per day, for breakthrough pain, for more than 3 days during the baseline period, or if their maintenance opioid dosing regimen was modified during this period; (11)Patients with severe cancerous pain (e.g., typical average daily pain intensity rating of 7 to 10 on a numerical rating scales (NRS; 0 [no pain] to 10 [the worst pain possible]) after the utility of routine dose and frequency of opioids) refractory to opioid therapy; (12) Patients with a history of opioid discontinuation due to severe adverse events or patients that are suspected to discontinue opioid use due to the potential risk of adverse events; (13)Patients that received an opioid receptor antagonist or agonist within one month of the screening, or those who are scheduled to receive such

therapy during the study; (14) Patients with a history of nerve neurolysis; (15) Patients with severe cognitive impairment, aphasia, or psychiatric disorders; abdominal aortic aneurysm; hepatomegaly; or splenomegaly; (16) Patients that have received acupuncture within three months of the screening; (17)Other patients who are considered ineligible for the study by the investigator on the basis of concomitant therapy and medical findings.

### 2.4.2.3 Subject Withdrawals

There will be at least one oncologist or gastroenterologist in each center. They will assess the severe adverse events (SAEs) and then determine whether the participant to continue or terminate the trial. Subjects may leave the study at their own discretion, or the investigator may determine whether it is in the best interest of subjects to withdraw from the trial due to worsening of symptoms, or the occurrence of a serious adverse event.

### 2.4.2.4 Subject Recruitment, Screen and Grouping Assignment

Participants with cancer will be publicly recruited from inpatient and outpatient departments through posters and networks. Research assistants of each site will preliminarily screen the participants by recording their disease condition, history of the disease and treatment, and the demographic data. An oncologist or gastroenterologist of each site will take charge of the diagnosis and the differential diagnosis of the OIC. Potential participants will fill out a 1-week patient diary to record bowel movements, the stool consistency, degree of difficulty in defecation, the rescue medicine drugs and duration of usage, and the intensity of cancerous pain, etc. Eligible participants then will be randomized to EA or SA group. Acupuncturists are in charge of the participants' group assignment, and the EA or SA treatments. They are also responsible for the assessment of safety during treatment. During the trial, the professional evaluators of each site will instruct the participants how to fill in patients' self- assessment related to the trial and their patient diaries and the evaluators will record the data on the case report form (CRF) through the whole trial period. The subject flow was shown in Figure 1.

[figure not shown]

Figure 1. Subject flow

### 2.4.3 Trial flow chart

[figure not shown]
The trial flow chart was shown in Figure 2.

	Study Period				
	Baseline	Allocation	Treatment	Follow-up	
Enrollment	Weeks -1	Week 0	Weeks 1 to 8	Weeks 13 to 16	
Eligibility criteria	×				
Demography characteristics	×				
Disease history of cancer	×				
Disease history of OIC and constipation	×				
Eligibility screen	×				
Informed consent	×				
Allocation		×			
Interventions					
Electroacupuncture			×		
Sham electroacupuncture			×		
Assessments					
SBMs	×		×	×	
CSBMs	×		×	×	

Mean Bristol Stool Form Scale score for stool consistency of SBM	×	×	×
Mean score for straining of SBM	×	×	×
PAC-SYM total score and subscale scores	×	×	×
PAC-QOL total score and subscale scores	×	×	×
Patients' global assessment of treatment efficacy		X	×
Rescue medicine usage	×	×	×(weeks 9 -16)
Opioid usage	×	×	× (weeks 9-16)
Patients' expectation of the acupuncture efficacy	×		
Blinding assessment		X	
Cancer pain		×	×
Adverse events	×	×	× (weeks 9-16)
Safety assessment	×	×	× (weeks 9-16)

Abbreviations: OIC, Opioid-induced constipation; SBMs, spontaneous bowel movements; CSBMs, complete spontaneous bowel movements; PAC-SYM, Patient Assessment of Constipation-Symptom questionnaires; PAC-QOL, Patient Assessment of Constipation-Quality of Life questionnaires.

Figure 3. The schedule of enrollment, interventions, and assessments

### 2.4.4 Outcomes Measurement

### 2.4.4.1 Primary Outcome

The primary outcome will be the the proportion of responders, defined as a patient that has  $\geq 3$  SBMs/wk and  $\geq$  increase of 1 SBM from baseline simultaneously for at least 6 out of 8 weeks of the treatment period. SBM refers to a bowel movement that occurred without medication or assistance within the previous 24 hours. When a bowel movement occurs within 24 hours of the use of an optional assisted method (rescue medication or other bowel-treatment regimens) for defecation, it is not regarded as an SBM.

[figure not shown]
Every participant will be required to keep a diary 13 weeks: baseline (run-out period before randomization), 8 weeks of treatment, and 4 weeks of follow-up. Diary entries include the frequency of bowel movements, the consistency of the stool, the difficulty in defecating, the rescue medicine drugs applied and their duration, and the intensity of the cancer pain. During the treatment period, the diary will be collected weekly, and during the follow-up period, it will be collected at the end of week 16. The outcome evaluators will examine the diary content and determine the SBM and frequency accordingly.

### 2.4.4.2 Secondary Outcomes

- (1) Changes in the mean weekly SBMs from the baseline during weeks 1-8 and weeks 13-16. The mean weekly SBMs equals the total frequency of SBMs divided by the numbers of week(s) recorded. Assessment time frame: at baseline, over weeks 1-8 and 13-16.
- (2) The proportion of patients with ≥3 mean weekly SBMs during weeks 1-8 and weeks 13-16. Assessment time frame: at baseline, over weeks 1-8 and 13-16.
- (3) The proportion of patients with an increase of ≥1 mean weekly SBM from the baseline during weeks 1-8 and weeks 13-16. Assessment time frame: at baseline, over weeks 1-8 and 13-16.
- (4) A change in the mean weekly CSBMs from the baseline during weeks 1-8 and weeks 13-16. A CSBM is defined as an SBM with the feeling of complete evacuation. The mean weekly CSBMs equals the total frequency of CSBMs divided by number of week(s)

recorded. Assessment time frame: at baseline, over weeks 1-8 and 13-16.

- (5) The proportion of patients with ≥3 mean weekly CSBMs during weeks 1-8 and weeks 13-16. Assessment time frame: at baseline, over weeks 1-8 and 13-16.
- (6) The proportion of patients with an increase of ≥1 mean weekly CSBM from the baseline during weeks 1-8 and weeks 13-16. Assessment time frame: at baseline, over weeks 1-8 and 13-16.
- (7) A change in the mean Bristol Stool Form Scale score for stool consistency of SBMs from the baseline during weeks 1-8 and weeks 13-16. For stool consistency, each patient will be asked to record their stool consistency according to the Bristol Stool Form Scale on the following seven points scale (scored from 1 to 7 for stool types 1 to 7, respectively). Assessment time frame: at baseline, over weeks 1-8 and 13-16.

- Type 1: Separate hard lumps, like nuts (hard to pass)
- Type 2: Sausage-shaped, but lumpy
- Type 3: Like a sausage but with cracks on its surface
- Type 4: Like a sausage or snake, smooth and soft
- Type 5: Soft blobs with clear cut edges (passed easily)
- Type 6: Fluffy pieces with ragged edges, a mushy stool
- Type 7: Watery, no solid pieces. Entirely liquid

- (8) A change in the mean score for the straining of SBMs from the baseline during weeks 1-8 and weeks 13-16. For assessment of the straining of SBMs, each patient will be asked to rate his/her score of straining, using the following five-point scale: not at all difficult (0), a little bit difficult (1), moderately difficult (2), quite a bit difficult (3), extremely difficult (4). Assessment time frame: baseline, over weeks 1-8 and 13-16.
  - (9)A change in the total and subscale score of the Patient Assessment of

Constipation-Symptom (PAC-SYM) questionnaire from the baseline at weeks 8 and 16. The PAC-SYM is a questionnaire used to evaluate the severity of chronic constipation in the past 2 weeks. It consists of 12 items, which are subdivided into abdominal (4 items), rectal (3 items), and stool (5 items) scales.34 36 The score of each item ranges from 0 to 4, with 0 = symptom absent, 1 = mild, 2 = moderate, 3 = severe and 4 = very severe. Lower scores indicate a lower symptom burden. Each subscale score will be calculated as the mean of the completed items for that subscale. The total score will be calculated as the mean of all completed items. In this trial, the Chinese version of PAC-SYM, which has been validated to have a satisfactory psychometric property, will be used. Assessment time frame: at baseline, at weeks 8 and 16.

- (10) A change in the total and subscale scores of the Patient Assessment of Constipation-Quality of Life (PAC-QOL) questionnaires from the baseline at weeks 8 and 16. The PAC-QOL is a 28-item self-reported questionnaire to assess the burden of constipation on patients' everyday functioning and well-being in the 2 weeks (14 days) prior to assessment. This questionnaire is divided into four subscales: physical discomfort (items 1-4), psychosocial discomfort (items 5-12), worries/concerns (items 13-23), and satisfaction (items 24 to 28). Each of the item scores ranges from 0 (not at all) to 4 (extreme), with lower scores indicating a better quality of life. For each visit, individual subscale scores will be calculated as the mean of the completed items for that subscale. The total score will be calculated as the mean of all of the completed items. We will use the Chinese version of this test in our trial, which has been demonstrated to be a reliable and valid tool. Assessment time frame: at baseline, at weeks 8 and 16.
- (11) Patients' global assessment of treatment efficacy. Each patient will be asked to rate his/her efficacy of treatment using the following 7-point self-reporting scale: markedly worse (1), moderately worse (2), slightly worse (3), no change (4), slightly improved (5), moderately improved (6), markedly improved (7). Scales with seven response categories are easy to use and have shown a high reliability and validity. This questionnaire will be completed at week 8 and week 16. Assessment time frame: baseline, at weeks 8 and 16.
- (12) The proportion of patients using rescue medicine and the mean frequency of rescue medicine use per week during weeks 1-8 and weeks 9-16. Assessment time frame: at baseline, over weeks 1-8 and 13-16.

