4.4.4 Analyses for Secondary Outcomes

Efficacy analyses for all secondary outcomes will be performed in the ITT population, without imputation of missing data.

Continuous data will be described with the average, standard deviation, median, minimum value, and maximum value, whereas categorical data will be represented by percentages as appropriate.

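### Change scores for stool consistency and straining do not exist for patients with no SBM in the baseline week, so the stated ITT analysis does not hold for secondary outcomes (7) and (8)

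*Protocol*

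**What the plan says.** Outcome (7) in Protocol 2.4.4.2 is "A change in the mean Bristol Stool Form Scale score for stool consistency of SBMs from the baseline", and outcome (8) is "A change in the mean score for the straining of SBMs from the baseline during weeks 1-8 and weeks 13-16". Both are means over SBMs, not over all bowel movements.

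The baseline comes from a single diary week before randomization (Protocol 2.4.2.4): "Potential participants will fill out a 1-week patient diary to record bowel movements". Protocol 2.4.4.1 adds that when a movement follows rescue medication or another assisted method within 24 hours, "it is not regarded as an SBM".

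On eligibility, the Rome IV symptom list in Protocol 2.4.2.1 includes "fewer than three SBMs per week", which has an upper limit but no minimum and is one of five symptoms of which two are needed. Inclusion criterion (7) reads: "The SBM frequency of the patients must be 2 times a week when laxatives are not being taken".

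SAP 4.3 bases all analysis on every randomized patient. SAP 4.4.4 states: "Efficacy analyses for all secondary outcomes will be performed in the ITT population, without imputation of missing data". SAP 4.4.1 names the two-sample t-test, or the Wilcoxon rank-sum test for markedly non-normal data, for continuous variables. Neither document says what to do with a week or window that holds no SBM. For PAC-SYM and PAC-QOL, by contrast, the protocol does say how to score when some items are not completed.

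**The concern.** A mean over zero SBMs is undefined. The patient is not missing through a skipped visit or a lost diary: a fully completed diary can still yield no score. With no imputation and a two-sample test on change scores, such a patient cannot enter the comparison, yet the SAP describes it as covering everyone randomized.

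The situation is foreseeable, because the trial recruits for constipation and assisted movements do not count as SBMs. At stake are the precision of two secondary comparisons, the population to which they apply, and a choice of handling that would otherwise be made after the data are seen. The primary outcome and the SBM and CSBM count outcomes are not affected, since zero is a valid count.

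**Working it through.** **1. The plan's own figure.** The documents give no sample size or power for outcomes (7) and (8). The only figure is 100 patients for the primary responder outcome (Protocol 2.4.1.3: 14% on sham, difference 31.4 points, 90% power, two-sided 0.05, 20% loss). With unpooled variance:

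(1.960 + 1.282)² × (0.14 × 0.86 + 0.454 × 0.546) / 0.314² = 39.3, so 40 per arm; 40 / 0.8 = 50 per arm; 100 in total.

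This reproduces the plan's figure, and the present point does not touch it.

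**2. When the change score exists.** Change = (sum of scores in window / SBMs in window) − (sum of scores in baseline week / SBMs in baseline week). Both denominators must be at least 1. A zero in the baseline week gives 0/0 whatever is recorded later.

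**3. What the SAP then does.** No change score, no imputation (SAP 4.4.4), and a two-sample test (SAP 4.4.1): the patient drops out of the test. SAP 4.3 says that all randomized patients are analysed. Both cannot be true for these two outcomes. Protocol 8.1 lists repeated measures analysis among the possible methods, but no model is specified that would keep a patient without a baseline value.

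**4. How many, if criterion (7) means at most 2 SBMs a week.** The documents give no baseline distribution, so this is an assumption: a Poisson count with rate λ, truncated at 2. Then the share with none is f = 1 / (1 + λ + λ²/2). The standard error grows by 1/√(1 − f). The difference detectable with 80% power, in SD units, is (1.960 + 0.842) × √(2/n), with n = 50 × (1 − f) per arm.

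| λ | Mean count after truncation | f | Of 100 patients | SE factor | Detectable difference |
|---|---|---|---|---|---|
| 1.0 | 0.80 | 40% | 40 | 1.29 | 0.72 SD |
| 1.5 | 1.03 | 28% | 28 | 1.18 | 0.66 SD |
| 2.0 | 1.20 | 20% | 20 | 1.12 | 0.63 SD |
| 2.5 | 1.32 | 15% | 15 | 1.09 | 0.61 SD |

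With all 50 per arm the detectable difference is 0.56 SD. The table counts only the loss from an empty baseline week.

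**5. How many, if criterion (7) means exactly 2.** If it applies to the baseline week itself, almost nobody has zero. If it describes a usual frequency off laxatives, a diary week can still be empty: under an untruncated Poisson with rate 2, e⁻² = 13.5% (again an assumption), and assisted movements lower the SBM count further.

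**6. The later windows.** A patient with no SBM in weeks 1-8 or 13-16 also has no score. This loss arises after randomization and may depend on treatment, so unlike the baseline loss it can bias the comparison.

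**The case against.** The strongest reply is that the size cannot be established. Criterion (7) as printed gives a single number; a lost sign is plausible but cannot be confirmed, and the diary week precedes randomization, so on the literal reading few patients with an empty week would be enrolled. That stands, and it is why the size is given only as a range under a stated assumption.

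Three stronger readings are tempting, and the documents do not support them.

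- A reader might infer that the most constipated patients are removed and only milder ones compared. That is shown for SBM frequency alone. An empty week may reflect laxative use, and a patient with one or two hard, strained SBMs could be worse on exactly these two scales.
- A reader might infer that the baseline exclusion biases the treatment comparison. It rests on a value fixed before randomization, so by itself it does not.
- A reader might infer a specific loss of power. The trial is sized only for the responder outcome, and the documents give no effect size for these scores, so there is no planned power to lose.

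It is also fair to say that SAP 4.4.1 promises summaries of all variables and counts of missing values. The on-treatment scores would therefore still be tabulated and the gap would be visible. That reduces the harm, but it does not put the patients back into the test.

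**Conclusion.** The point holds, as a minor one. From the definitions and the no-imputation rule alone, a randomized patient with no SBM in the baseline week is excluded from the tests of outcomes (7) and (8), and the ITT description is inaccurate for those two outcomes. The consequences are lost precision and a narrower population, not bias from this source.

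The size is unknown. It is roughly 15% to 40% of patients if criterion (7) means at most 2 SBMs a week and a truncated Poisson with rate 1 to 2.5 is a fair description. It is few if the criterion means exactly 2 in the baseline week. The separate loss of patients with no SBM in a later window can bias the comparison and has to be reported and interpreted, because the model proposed below does not remove it.

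**What to change.** In SAP 4.4.4, for outcomes (7) and (8):

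- Compare the mean Bristol score and the mean straining score over weeks 1-8 and over weeks 13-16 between arms with a linear model containing treatment, the baseline score (set to a fixed constant where absent) and a missing-baseline indicator. Every patient with at least one SBM in the window is then kept. The indicator method is sound here because baseline missingness precedes randomization.
- Report by arm how many patients had no SBM in the baseline week, in weeks 1-8 and in weeks 13-16.
- State that the result applies only to patients with an SBM in the window, because that loss is post-randomization and may differ by arm.

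The cost is a few sentences of SAP text and one model per outcome and window. No extra data are needed. The small downside is that the estimate becomes an adjusted mean difference in place of a raw change.
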